## 6. Purpose of Research

The overall goal of this project is to assess the contribution of cues and spaced retrieval education on wayfinding ability and life space in persons with wayfinding impairment who live in long term care communities in a randomized controlled trial. We will select nine senior assisted living residences and recruit 137 residents identified as having wayfinding problems who can move themselves and communicate. We will randomize the facilities to one of three arms 1) Control (no changes); 2) Cued (salient environmental landmarks and signage placed at key decision points) plus staff training on use of the cues and 3) Cued plus Spaced- Retrieval education. Subject characteristics including mobility, demographic variables, activities of daily living, and cognitive ability will be measured along with life space mobility (spatial extent of mobility). We will test all subjects' wayfinding ability (primary outcome) and life space (secondary outcome) at baseline and at 1, 3, 6, and 12, months. We will compare wayfinding performance over time among the 3 trial arms.

The specific aims are:

Aim 1: To examine the effect of salient cues with and without spaced retrieval education on wayfinding ability initially and over time in older adults who have wayfinding deficits in long term care communities. HO1: Subjects will have improved wayfinding (faster, more accurate) in the cued condition versus the control condition at months 1, 3, 6, and 12; and post intervention compared to pre intervention.

H02: Subjects in the cued condition + Spaced Retrieval education will have improved wayfinding ability compared to the control and cue alone condition at times 1, 3, 6, and 12 months.

Aim 2: To determine the effects of salient visual cues and spaced retrieval training on life space.

H03: Subjects in the cued conditions will have larger life spaces than those in the control condition at times 1,3, 6 and 12 months.

H04: Wayfinding ability will be positively correlated with larger life space over time.

Exploratory Aim 3: To determine which subject characteristics are most amenable to the intervention; and which subject characteristics place persons at risk for less responsiveness to the intervention so that the intervention can be appropriately targeted.

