**Please provide justification for why the number of subjects to be recruited is appropriate.**

The sample size for this study was determined based on Specific Aim 1, Hypotheses H01 and H02 for the pairwise comparisons of the trial arms. In the prior R15-funded study of the PI, the effect size for the difference in wayfinding time observed under cue versus no cue condition was 0.42 (a reduction of 8 minutes on average, with a standard deviation of 19 minutes). In the proposed study, wayfinding will be measured at baseline, 1, 3, 6, and 12 months. Since baseline measure will be used as a covariate in the analysis of repeated measures of outcomes (see the analysis section), the adjusted standard deviation in this analysis would be smaller than unadjusted. Assuming correlation of 0.4 between pairs of repeated measures, the effect size adjusted for the design of the proposed trial and analysis strategy is 0.67, which would be detected with power 0.8 or greater in two-sided tests using 0.05 level of significance with the sample size of 36 per group. Next, this sample size was adjusted to account for clustering of participants within care communities using a conservative estimate of the intraclass correlation coefficient (ICC) of 0.0012. The resulting design effect factor is 1.042 yields the sample size requirement of 38 per group, or 114 total. Finally, to account for projected 20% attrition, 137 participants will need to be recruited. This corresponds to the average recruitment goal of 11 participants per care community. The participating care communities stated that they have 10 to 30 available participants satisfying the inclusion criteria; therefore the required sample size is feasible.

**Briefly describe the subject population characteristics (i.e., age ranges, and where appropriate, gender, ethnic background, and health status).**

Planned enrollment includes men and women 62 years and older. For NIH our enrollment table includes an ethnic and racial mix of subjects in alignment with the population in the cities in which the study is being conducted - however, the sample is a convenience sample.

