2. The IL communities will be randomly assigned to waves 1, 2 or 3 (three per wave). The AL communities will be assigned to wave
3. Three routes, which vary with respect to complexity (low, medium, and high complexity), will be chosen based on the space syntax assessment for each community using a computer program that calculates space syntax. Space syntax gives numerical values of complexity for routes in terms of length of path, number of path intersections, visibility of destinations, connectedness of spaces (direct connection versus indirect connection through intermediate spaces) and salience of existing cuing

(number, size, contrast, location and distinctiveness of cues). The rationale for choosing the routes based on space syntax is so that similarly complex routes can be compared among communities with different building design, and so that a range of complexity of routes is provided.

4. Subjects will be recruited and enrolled from each of the three communities prior to the intervention (see Human Subjects section).

5. After enrollment, the care communities will be randomized to either the control (Arm 1), Cued (Arm 2) or Cued Plus SR (Arm 3) condition. The rationale for randomizing after enrollment is to reduce potential selection bias due to the type of participants that agree to be in the study based on being in the intervention group or not.

6. At baseline, all enrolled subjects will undergo measurements of wayfinding ability, health, cognition, mobility and life space.

7. Arms 2 and 3 of the will have salient visual cues (colorful, familiar objects), including pictures, signage, statues and nature elements placed throughout the care community at key decision points (Figure 1). Arm 3 will additionally receive SR education, which uses a procedural memory cue over increasingly longer spaces of time. The control care communities will receive no change in décor or training (described below).

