8. Wayfinding performance (primary outcome) will be compared between the participants in the care communities repeatedly over a period of 12 months (baseline, 1, 3, 6 and 12 months). The rationale for the time frame of outcome measures is to determine the effects of the interventions initially and over time. This information will be essential to understanding the timing and dosage of the interventions. Most studies that examine wayfinding only look at initial learning or short term retention; we seek to address this problem by assessing the impact of the intervention over a sustained period of time. Subjects will have their life space (secondary outcome) measured via a questionnaire. In addition, one community from each arm (for a total of three communities) will have life space measured via a mobility tracking device at these time frames.

9. Randomization will occur in the same manner in Waves 2-4 with enrollment of residents from nine additional care communities (three in each Wave). Each Wave will have similar communities in terms of space syntax and level of care. Randomization in this manner, a control comparison group, and careful measurement of the complexity of the communities and the subjects' baseline characteristics will provide a rigorous and reproducible study.

Description of ARMS. ARM 1 is the control condition, in which there will be no modifications to décor or signage in the existing care community, and no education on wayfinding. However, subjects will receive the same testing that is provided for the other arms at the designated time periods. ARM 2 consists of adding cues to the environment along the routes being measured for wayfinding. The cues will be comprised of pictures, objects, and signage (described below). The care community staff, residents, and visitors will be given a brochure indicating the purpose for the cues and suggesting ways in which individuals can use the cues for wayfinding. ARM 3 is the cues + spaced retrieval education. This condition will have cues as in ARM 2 added to the care communities. In addition, a spaced retrieval (SR) memory intervention strategy will be implemented individually for each resident participating in the study to help them remember the presence and function of the environmental wayfinding cues.

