**Specific Aim 1** examines the effect of salient cues with and without spaced retrieval education on wayfinding ability. The statistical model #1 for the repeated measures of wayfinding ability at 1, 3, 6, and 12 months will include the following explanatory variables: wayfinding ability at baseline, time (with levels 1, 3, 6, 12 months), trial arm, and control variables measured at baseline (see the measures section). Time will be included as categorical variable with the above mentioned levels to model potentially non-linear (polygonal) changes in outcomes over time. For the first measure of wayfinding ability, average speed calculated as described in the measures section, this model will be implemented as a linear mixed effects (LME). It will also include random effect indicating facility as will all other statistical models. The LME model generalizes classical analysis of repeated measures and allows for data missing at random, time-varying covariates, and structured covariance matrix. The participants who completed at least one post-baseline assessment will be included in the analysis following the intent to treat principle. The second measure of wayfinding ability, the proportion of wrong turns, by definition takes values from the [0, 1] interval and will be analyzed using generalized LME with beta distributed errors. Beta distribution supported on [0, 1] interval is particularly suitable to this measure.

The essential parameter of interest in the statistical model #1 is associated with the trial arm variable. The least square (LS) means corresponding to this variable will be output from the model, and differences among them will be tested. The test of significance of the differences between LS means for cues versus control and cues + spaced retrieval education versus control will yield the formal test of hypothesis H01. The test of the significance of the differences between cues + spaced retrieval education versus cues alone will yield the formal test of hypothesis H02. After testing the main trial arm effects, time by trial arm interaction will be added to the statistical models to explore whether intervention effects change as time progresses. The significance of the interaction term will be assessed, and differences in LS means by trial arm at each time point will be tested to determine the immediate and sustained effects.

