**Specific Aim 2** tests the effect of the active trial arms on the secondary outcome of life space. Statistical model #1 will be modified to include the repeated measures of life space as the

dependent variable, and hypothesis H03 will be tested by comparing the LS means for the two active arms. This will first be done using *Tinetti's Nursing Home Life-Space Diameter* measure for all participants.

**Handling of missing data and alternative analytical approaches.** The patterns of missing data will be evaluated using SAS PROC MI to determine if the assumption of missing at random (MAR) is reasonable. The analysis techniques for Aims 1-3 allow for MAR mechanism. If patterns of missing data indicate potential missing not random (MNAR) mechanism, then models describing missing mechanisms will be considered (e.g. pattern-mixture models). Since MNAR or MAR assumptions are not directly testable, we will employ sensitivity analyses to investigate how the results would or would not change under pattern-mixture or other models for the missing mechanism.

**Strategies for Multiple Inferences.** Because the study hypotheses were stated a-priori, adjustments for multiplicity are not necessary in the analyses for the main study Aims 1 and 2. In additional analyses for the exploratory Aim 3, false discovery rate will be controlled using Hochberg or Benjamini-Hochberg procedures. Since adjustments for multiplicity are controversial, the results will be presented both unadjusted and adjusted.

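### The SAP's named test of H03 (life space, cued arms versus control) compares the two active arms with each other and leaves control out

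*SAP*

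**What the plan says.** Protocol section 6 (Purpose of Research, Aim 2) states H03: "Subjects in the cued conditions will have larger life spaces than those in the control condition at times 1,3, 6 and 12 months". The comparator is control.

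The SAP, Specific Aim 2, keeps statistical model #1, makes life space the dependent variable, and then says that "hypothesis H03 will be tested by comparing the LS means for the two active arms". No comparator outside those two arms is given.

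Under Specific Aim 1 the SAP says which contrast tests which hypothesis:

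- H01, which like H03 sets cued conditions against control: the "differences between LS means for cues versus control and cues + spaced retrieval education versus control will yield the formal test of hypothesis H01".
- H02: the "differences between cues + spaced retrieval education versus cues alone will yield the formal test of hypothesis H02".

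The design has three arms. Protocol section 8d says that "the care communities will be randomized to either the control (Arm 1), Cued (Arm 2) or Cued Plus SR (Arm 3) condition". The same section says of the control arm that "subjects will receive the same testing that is provided for the other arms at the designated time periods", so life space is measured there too.

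**The concern.** With three arms, a comparison of the two active arms cannot show whether either differs from control. An analyst who follows the SAP literally would report, as the formal test of the secondary outcome, a result about the added value of spaced retrieval. H03 does not ask that question.

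Two errors could follow. Cues could enlarge life space in both cued arms and the formal test would usually show no difference. Or the two cued arms could differ from each other with no average benefit over control, and the formal test could be significant.

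Designation matters because the SAP declines multiplicity adjustment for Aims 1 and 2 on the ground that the hypotheses were fixed in advance. That argument needs a named test that matches the stated hypothesis. If comparisons with control are substituted at the analysis stage, the reported H03 test is no longer the pre-specified one.

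**Working it through.** **1. Contrast weights.** Order the arm LS means as (control, cues, cues + SR).

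| Test | Source | Weights |
|---|---|---|
| H01 | SAP, Specific Aim 1 | (-1, +1, 0) and (-1, 0, +1) |
| H02 | SAP, Specific Aim 1 | (0, -1, +1) |
| H03 as worded | SAP, Specific Aim 2 | (0, -1, +1) |
| H03 as hypothesised | Protocol section 6 | (-1, +1, 0) and (-1, 0, +1), or pooled (-1, 0.5, 0.5) |

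The worded H03 contrast has the SAP's H02 weights, applied to life space instead of wayfinding.

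**2. Equal benefit in both cued arms.** Let both exceed control by d. The worded contrast has expected value 0 × 0 - d + d = 0 for every d. A valid two-sided 0.05 test therefore rejects 5% of the time. This result needs no assumption about d, the SD or the clustering.

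**3. The plan's own sample-size figure.** The documents give no effect size or SD for life space: "The sample size for this study was determined based on Specific Aim 1, Hypotheses H01 and H02". For wayfinding, 8/19 = 0.42. With four repeated measures, correlation 0.4 and baseline adjustment, the variance factor is (1 + 3 × 0.4)/4 - 0.4² = 0.55 - 0.16 = 0.39, and 0.42/√0.39 = 0.67. At 36 per group a two-sided 0.05 t test has power 0.80. The stated 36 is reproduced. The design effect is 1 + 35 × 0.0012 = 1.042, and 36 × 1.042 = 37.5, which rounds up to 38.

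**4. What a comparison with control could detect (illustration).** Assumptions: 38 per arm, design effect 1.042, SD 1, and standardised life-space gains that the documents do not supply. The values 0.42 and 0.67 are borrowed from wayfinding; the first is unadjusted, the second adjusted for baseline and repeated measures. Effective n = 38/1.042 = 36.5 per arm. The noncentrality is d × √(36.5/2); at d = 0.67 it is 2.86. Two reference distributions are shown: 74 df (individual level) and 9 df (12 communities minus 3 arms, since communities are randomised).

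| Assumed gain d in both cued arms | Worded contrast | Each versus-control contrast, 74 df | Each versus-control contrast, 9 df |
|---|---|---|---|
| 0.20 | 0.05 | 0.13 | 0.12 |
| 0.42 | 0.05 | 0.42 | 0.36 |
| 0.50 | 0.05 | 0.56 | 0.48 |
| 0.67 | 0.05 | 0.81 | 0.72 |

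**5. The reverse case.** Suppose cues + SR is 0.335 SD above control and cues alone 0.335 SD below. The average cued effect is (0.335 - 0.335)/2 = 0, but the worded contrast estimates 0.335 + 0.335 = 0.67. It would reject with probability 0.81 (74 df) or 0.72 (9 df).

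**The case against.** The best reply is that the sentence is elliptical. The Aim 2 paragraph opens by speaking of the effect of the active arms, which suggests a control reference. Model #1 keeps its arm variable, and the Aim 1 text says in general terms that differences among the arm LS means will be tested. If that carries over, the life-space differences from control are already planned and only the H03 label is misplaced. The public Aim 2 text may also be incomplete, since it announces a first step with no second.

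A dropped reference to control is quite possible, and the needed contrasts are available from the model. But availability is not designation. After the general statement, the SAP says which difference is the formal test of each hypothesis. It writes out control for H01 and does not for H03.

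Three narrower points stand:

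- The overlap with H02 is in the arm weights of the SAP's test, not in the outcome. The protocol's own H02 is also wider, since it says the cues + SR arm "will have improved wayfinding ability compared to the control and cue alone condition at times 1, 3, 6, and 12 months".
- Equal benefit in both cued arms is only one scenario. If spaced retrieval adds to life space, the worded contrast can reject, but it would still be answering a different question.
- The power figures are illustrative, and the 74 df column is optimistic for a design with 12 randomised communities.

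None of these changes the result in step 2. The issue is confined to one secondary hypothesis in a trial that describes itself as a pilot.

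**Conclusion.** The concern holds. As written, the SAP's test of H03 does not test the H03 stated in the protocol. The mismatch follows from the two texts alone, and so does the 5% rejection rate under equal benefit, given a valid test. The power of a comparison with control (about 0.36 to 0.42 at an assumed 0.42 SD, and 0.72 to 0.81 at an assumed 0.67 SD) rests on borrowed effect sizes and only gives a sense of scale.

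The error lies in the named contrast. Model #1, data collection in the control arm and the primary Aim 1 tests are unaffected. It should be fixed before analysis.

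**What to change.** Replace the H03 sentence under Specific Aim 2 with wording such as: *H03 will be tested by the LS-mean differences cues minus control and cues + spaced retrieval minus control, as for H01, with baseline life space as the baseline covariate; the difference between cues + spaced retrieval and cues alone is supportive.*

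The baseline covariate follows from changing the outcome of model #1, which already adjusts for the baseline value of its outcome. A single contrast of the pooled cued arms against control would also match H03. If two contrasts are kept, the SAP should say whether one or both must succeed. Either choice should be recorded before life-space results by arm are seen.

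The cost is one sentence or two of SAP text. Life space is already collected in all three arms, so no data or participants are added.

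### Stating the hypotheses in advance does not justify three unadjusted arm contrasts on two unranked wayfinding measures: if any one success counts, the false-positive chance is about 12% on one measure and about 20% to 23% over both

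*SAP*

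**What the plan says.** Protocol section 8d (Study Outcomes) names wayfinding performance as the primary outcome and lists two measures under it: time or speed over the route, and errors as a percentage of possible turns. Neither is put first. A wrong turn is corrected and adds 2 minutes to the time, so errors already feed into the speed measure.

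The SAP (Specific Aim 1) compares arm LS means from model #1. It says the differences for "cues versus control and cues + spaced retrieval education versus control will yield the formal test of hypothesis H01". A third contrast, the combined arm against cues alone, tests H02. The model is first described for average speed. "The second measure of wayfinding ability, the proportion of wrong turns" then gets its own beta model, and the contrasts are described once for both measures.

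Under Strategies for Multiple Inferences, the SAP gives this rule: "Because the study hypotheses were stated a-priori, adjustments for multiplicity are not necessary in the analyses for the main study Aims 1 and 2". Adjustment is planned only for exploratory Aim 3, and the promise to show results both ways follows directly on that. There is no overall test acting as a gate, no hierarchy, and no rule on how many contrasts or measures must succeed.

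The significance level appears in Protocol section 7a, which sizes the trial for "Hypotheses H01 and H02 for the pairwise comparisons of the trial arms", with power of at least 0.8 "in two-sided tests using 0.05 level of significance" and no split of alpha.

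**The concern.** The reason given for the waiver does not support it. A prespecified set of six tests at 0.05 each has the same joint error as any other set of six. Prespecification only fixes which six they are. Because the measures are unranked and no success rule is given, the plan as written lets any one of six results be reported as support for Aim 1. The reader of a positive report could not tell whether the risk attached to the claim was 5% or several times that. The SAP is also uneven: the exploratory aim is adjusted, while the aim for which the trial was powered is not.

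**Working it through.** **Inputs.** Three arms of equal planned size. Three contrasts and two measures (SAP, Specific Aim 1). Two-sided 0.05 per test, effect size 0.67 and 36 per arm (Protocol 7a). The correlation between the two measures is not given, so it is an assumption, shown from 0 to 1.

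**The plan's own figure.** The starting effect is "0.42 (a reduction of 8 minutes on average, with a standard deviation of 19 minutes" and the adjustment is made "Assuming correlation of 0.4 between pairs of repeated measures". With the mean of four follow-ups and baseline as covariate, the effect is (8/19) / √[(1 + 3×0.4)/4 − 0.4²] = 0.421/√0.39 = 0.67. A two-sample t test with 36 per arm at two-sided 0.05 then has power 0.8005. Next, 36 × 1.042 = 37.5, so 38 per arm and 114 in all, and 114 × 1.2 = 137. The sample size therefore reproduces as that of a single unadjusted pairwise contrast.

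**Three contrasts, one measure, all arms equal.** At least one |z| exceeds 1.96 exactly when the range of the three standardised arm means exceeds 1.96√2 = 2.77. The studentized-range tail for three means is 0.122. With t tests on 6 to 9 facility-level degrees of freedom it is 0.109 to 0.113.

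**Both measures.** If they are independent, 1 − (1 − 0.122)² = 0.23. Simulation (1,000,000 draws) for other correlations:

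| Correlation | Any of 6, either direction | Any of 6, hypothesised direction |
|---|---|---|
| 0 | 22.9% | 12.7% |
| 0.3 | 22.3% | 12.2% |
| 0.5 | 21.3% | 11.6% |
| 0.7 | 19.6% | 10.7% |
| 0.9 | 16.8% | 9.1% |
| 1 (same as one measure) | 12.2% | 6.6% |

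The nominal values are 5% and 2.5%. Treating all six tests as independent would give 1 − 0.95⁶ = 26.5%, which is too high because the contrasts share arms.

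**By hypothesis.** H01 on one measure is 9.1% if either contrast suffices and 0.9% if both must be significant. H01 over both measures is 9.1% to 17.2% if any contrast suffices, and H02 over both is 5.0% to 9.8%.

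**Price of an overall-test gate.** The option is a 2-df arm test at 0.05, then pairwise t tests at 0.05, with 36 per arm. Its error is 5.0% per measure. Power with and without the gate, for true arm means (control, cues, cues + SR) in SD units:

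| Pattern | Contrast | No gate | Gate | No gate, 9 df | Gate, 9 df |
|---|---|---|---|---|---|
| (0, 0.67, 0.67) | either active vs control | 0.80 | 0.76 | 0.72 | 0.64 |
| (0, 0.335, 0.67) | cues + SR vs control | 0.80 | 0.70 | 0.72 | 0.56 |
| (0, 0.67, 1.34) | cues vs control | 0.80 | 0.80 | 0.72 | 0.72 |

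The 9 degrees of freedom are illustrative (12 communities less 3 arms). Bonferroni over three contrasts gives about 0.66, against 0.80 without adjustment.

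**Gate across measures.** Suppose both active arms improve speed by 0.67, nothing affects wrong turns, the measures are independent, and any significant speed contrast opens the wrong-turns tests. The error over both measures is then about 9%.

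**The case against.** **It is a pilot, and the choice is open.** Protocol section 8d calls the study a pilot RCT, and the SAP discloses the waiver. Whether separately stated hypotheses need family-wise control is partly a matter of judgement. This stands, and it bears on severity. It does not rescue the stated rationale: the trial is powered for H01 and H02, and the SAP calls these formal tests.

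**The 23% is conditional.** A reader might infer that Aim 1 carries a 23% error rate. The documents do not support that as a fixed figure. It pools H01 and H02, counts significant harm as a claim, takes the measures as uncorrelated and lets one test suffice. The 2-minute penalty makes some correlation likely, and the SAP's wording for H01 can be read as needing both contrasts, in which case H01 on one measure is about 1%. Nor is 23% a ceiling, since by-visit contrasts are also tested and are not counted here.

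**Adjusted results are already promised.** The sentence is not expressly limited to Aim 3. But it follows the Aim 3 methods, and no adjustment method is given for Aims 1 and 2, where adjustment is said to be unnecessary.

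**A gate would solve it almost free.** With three arms, a reader might infer that an overall test first costs next to nothing, or at most the 4 points lost when the active arms are equal. That is not the least favourable pattern. If cues alone has half the effect, the loss is about 11 points, and about 16 with 9 facility-level degrees of freedom. Nor does the gate hold 5% over both measures if any speed contrast opens the second. It is a legitimate option, not an obvious correction.

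**Conclusion.** The point holds. The waiver rests on a reason that does not control error, and the primary outcome has six unranked tests with no success rule. The size is about 12% on one measure (about 11% with few facility-level degrees of freedom) and about 20% to 23% over both at an assumed correlation of 0.7 to 0, falling towards 12% as the correlation approaches 1. In the hypothesised direction it is about 7% to 13% against 2.5%. These figures assume that all three arms are equal, arm sizes are equal, each test is at two-sided 0.05, and any single success counts. The documents neither state nor exclude the last of these. The plan should be changed, but the documents do not show that full family-wise control is obligatory in this pilot.

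**What to change.** 1. In the SAP and Protocol section 8d, name average speed as the single primary wayfinding measure. This fits the sample size, which rests on wayfinding time. Make the proportion of wrong turns a key secondary measure that cannot by itself support an Aim 1 claim. This removes the near-doubling across measures.
2. State whether H01 is met by one significant active-versus-control contrast or needs both.
3. Delete the a-priori rationale. Report the three speed contrasts both unadjusted and multiplicity-adjusted, as the SAP already does for Aim 3, with the adjustment method named in advance.

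**Cost.** Wording only, with no loss of power on the unadjusted speed contrasts. The downside is that an effect on wrong turns without one on speed would be supportive evidence only. The choice of speed is the investigators' to confirm.

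**Option.** If strict 5% control on speed is wanted, an overall 2-df arm test before the pairwise tests will give it. It costs 0 to about 11 points of power in the patterns checked at 36 per arm, and up to about 16 with 9 facility-level degrees of freedom. The investigators should weigh that before adopting it.
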